Aim 1: To assess the needs and preferences of disadvantaged patients and safety net health care providers regarding the use of health IT for communicating PGHD and PROs.

Aim 1 Research Questions: What specific features in COTS solutions meet the needs and preferences of disadvantaged patients for communicating PGHD and PROs to their providers? What PGHD and PROs are deemed most important by providers and patients for improving health care and health outcomes?

Answering these questions will inform health IT solution selection, design, usability, and utility; assist with prioritizing PGHD and PROs collection by data element and measure type; and identify potential discrepancies between patients' and providers' perceptions of PGHD and PROs importance.

Aim 2: To demonstrate the feasibility of PGHD and PROs collection through COTS health IT solutions in a patient-centered pilot intervention for weight management among disadvantaged patients.

Aim 2 Hypothesis: Providing PGHD and PROs through COTS solutions will improve engagement among disadvantaged patients. Secondary outcomes include improving key health indicators (e.g., weight, physical activity) and PROMs (e.g., quality of life, mental health symptoms).

Weight management is important in delaying, averting, and reducing the effects of multiple chronic diseases, including diabetes, hypertension, and obesity. A weight management-related intervention also serves as an effective test of PGHD and PROMs collection, due to the existence of numerous COTS solutions which use different methods for tracking common data elements related to weight, physical activity, and fitness.

Aim 3: To create an ontology mapping and set of interoperability resources which can be used to support integration of PGHD and PRO into clinical information systems.

Aim 3 Hypothesis: PGHD and PROs can be characterized by distinct types, elements, and structures which, once described, may be modeled and mapped to existing vocabularies for health data management.

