Methods. Recruited participants will be randomized to one of two arms, intervention or control. Both intervention and control groups will engage in a 16-week program where they will receive regular health promotion messaging about (a) food, nutrition, and diet; and (b) exercise and physical activity. Existing content in these topic areas is available in a DH text messaging library aligned with the Centers for Disease Control and Prevention's (CDC) evidence-based Diabetes Prevention Program (80), for which a previous study demonstrated clinical efficacy (116). Additional messaging content will be informed by focus group and interview findings. Intervention patients will be asked to track PGHD elements related to weight management through a mobile health app loaded on their phones and/or through using a fitness tracker, depending on patient preference, and to share that information with the research team. If intervention patients do not have a fitness tracker, a low-cost COTS option will be provided for them. Both iOS and Android phone options will be

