supported. The app will be selected from a limited set of well-established options such as LoseIt!, MyFitnessPal, Apple Health, or Google Fit. The PGHD requested through active tracking and patient data entry will include self-monitoring elements previously shown to be successful at encouraging obesity-related behavioral change (129), such as calorie intake, food logging, minutes of physical activity, and weight. Patient contextual data requested through passive tracking may include items such as geographic location, sleep quality, and heart rate. Any additional data requested will be determined based on the results of Aim 1 and in consultation with the research team to identify social, behavioral, and clinically relevant information. Both intervention and control patients will be weighed on a clinic scale and asked to complete three PROMs pre- and post-intervention. These include the short form of the Patient Activation Measure (PAM-13), which is a validated PROM that assesses an individual's knowledge, skills and confidence in self-management behaviors (35, 36); the HRQOL-4, which is a validated PROM that assesses patients' overall physical and mental health status over the prior 30 days (37); and the Healthy Days Symptoms Module, which is a validated PROM that assesses physical and mental health symptoms which may have affected patients' lives over the prior 30 days (37). Intervention patients will also be asked to complete the three PROMs once each per month over the course of the 16-week intervention by email, online web form, text message, or app-based private message. Only privately submitted PROM data will be used in analysis, to protect patient privacy and to avoid social desirability bias due to self-curation behaviors associated with public reporting. One PROM will be collected per week, to avoid overburdening patients while ensuring a monthly collection of PROM data. The fourth week will include a simple check-in request, to maintain the weekly communication pattern. PGHD and PROs data will be extracted from shared systems, online forms, and messages as appropriate and placed into a REDCap (130) research database created for the project. These data will also be made available to and actionable by DH providers monthly through manual transfer to practice-standard patient-reported data forms and subsequent entry into the EHR. As this is a feasibility study, automated data exchange is beyond the scope of this initial project; however, the product of Specific Aim 3 will support future automated integration.

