
Outcomes and measures. The primary outcome of interest for the RCT is *patient engagement*. This outcome will be measured by patient response rates to data requests; by the frequency of unprompted messages sent by patients to research personnel; and by performance on the PAM-13. Secondary outcomes include weight loss and performance on the HRQOL-4 and Healthy Days Symptoms PROMs pre- and post-intervention. Weight loss will be assessed as change in body mass index (BMI) and absolute percent weight.

Data Analysis. Descriptive statistics will be computed for participant demographic characteristics (e.g., age, gender, race/ethnicity). Group differences (intervention vs. control) will be evaluated to ensure that the random group assignments were similar. If statistically significant differences ($p < 0.05$) are found between the groups for demographic or baseline measures, these will be controlled for in subsequent analyses. Logistic regression or the Chi-square test of proportions will be used to test differences in response rates and PROM scores between the RCT intervention and control groups. The distribution of the number of unprompted messages will be assessed and either analyzed using Poisson regression or dichotomized based on a clinically relevant cut-off and analyzed with either logistic regression or the Chi-square test of Proportions. Weight loss will be analyzed using the most appropriate and parsimonious multivariable regression technique, based on the nature of the outcome variable (e.g., continuous, time-varying, dichotomous, etc.). Fuzzy-set QCA will be conducted to examine the impact of factors identified through work conducted under Specific Aim 1.

Power. A total sample size of 256 patients is necessary to detect a proportional difference of 20% (0.55 intervention; 0.40 control) in the primary outcome between the intervention and control groups with 90% power ($\alpha = 0.05$). A sample size of 192 patients would be needed at 80% power. Given the nature of this feasibility study, we will attempt to recruit 300 patients for the RCT, but will consider the study adequately powered with 200 patients enrolled (100 intervention, 100 control). This also allows for some loss to follow-up.

3.4.3. Specific Aim 3. To create an ontology mapping and set of interoperability resources which can be used to support integration of PGHD and PROs into clinical information systems.

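### Response to data requests is tested between arms as a measure of the primary outcome, but the in-programme requests are described for the intervention arm only and the test is not limited to requests both arms receive

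*Combined protocol and SAP*

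**What the plan says.** Section 3.4.2, Outcomes and measures, makes patient engagement the primary outcome and gives it three measures: response rates, unprompted messages and PAM-13. Of the first it says "This outcome will be measured by patient response rates to data requests". The Data Analysis paragraph uses logistic regression or a chi-square test to "test differences in response rates and PROM scores between the RCT intervention and control groups".

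The Methods paragraphs of the same section describe who is asked for what:

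- Both arms, during the programme: "Both intervention and control groups will engage in a 16-week program where they will receive regular health promotion messaging". No data request is described here.
- Intervention arm, PGHD: "Intervention patients will be asked to track PGHD elements related to weight management through a mobile health app loaded on their phones".
- Intervention arm, PROMs: "Intervention patients will also be asked to complete the three PROMs once each per month over the course of the 16-week intervention".
- Weekly schedule: "One PROM will be collected per week, to avoid overburdening patients while ensuring a monthly collection of PROM data". The fourth week carries a check-in. These two sentences name no arm, but they follow directly from the intervention-only monthly PROMs.
- Both arms, before and after the programme: a clinic weighing and the three PROMs.

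The plan does not define a data request, the denominator of the response rate, or what makes a patient a responder.

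**The concern.** A between-arm test of response needs a set of requests that both arms receive. Such a set exists here, but the plan does not tie the test to it. The wording points towards a wider set: "The PGHD requested through active tracking and patient data entry will include self-monitoring elements", and the fourth-week check-in is also called a request. Read plainly, the measure includes items that controls are not described as receiving.

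There is also a circularity. The Aim 2 hypothesis is that "Providing PGHD and PROs through COTS solutions will improve engagement among disadvantaged patients", so supplying PGHD and PROs is the exposure. Counting responses to those same requests as the outcome partly counts the intervention.

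At stake is one of the three measures of the primary outcome. An arm difference could appear, or be hidden, with no true difference in responsiveness. Its size and sign would depend on a definition that could be chosen after the data are seen.

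**Working it through.** **Plan's own figures.** The plan gives no request count or response-rate definition to reproduce. Its power statement (0.55 against 0.40; 256 patients at 90% power, 192 at 80%) is not tied to any of the three measures. The pooled-variance formula, two-sided 0.05, gives 462 and 346 for those proportions. That is a separate matter, and nothing below rests on it.

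**Requests per patient** (Section 3.4.2, Methods). PGHD requests, whose number is not stated, and the weighing are left out.

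- In-programme cycles: 16 weeks / 4 = 4.
- In-programme prompts: 4 × 3 PROMs + 4 × 1 check-in = 12 + 4 = 16.
- Shared prompts: 3 before + 3 after = 6.
- All prompts: 16 + 6 = 22 intervention, 6 control.
- After baseline: 16 + 3 = 19 intervention, 3 control.

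This assumes that check-ins go to the intervention arm only and that the last monthly PROMs are separate from the post-intervention PROMs. If controls also get check-ins, the after-baseline count is 19 against 3 + 4 = 7. If the last monthly PROMs serve as the post-intervention PROMs, it is 9 + 3 + 4 = 16 against 3.

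**Per-patient definitions, no true difference.** The tests named need a binary outcome, and the plan states no cut-off, so three are assumed. Let X ~ Binomial(n, p) with the same p in both arms. The proportion of responders is P(X ≥ k). For p = 0.55 and 19 against 3:

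| Definition | Cut-off k (intervention, control) | Intervention | Control | Gap, points |
|---|---|---|---|---|
| Any answered | 1, 1 | 1.000 | 0.909 | +9 |
| At least half | 10, 2 | 0.671 | 0.575 | +10 |
| At least 80% | 16, 3 | 0.008 | 0.166 | -16 |

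For at least half, other values of p give:

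- p = 0.40: 0.186 against 0.352, a gap of -17 points.
- p = 0.68: 0.950 against 0.758, a gap of +19 points.

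**Sensitivity at p = 0.55** (any / at least half / at least 80%):

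- 22 against 6: +1 / +1 / -16.
- 19 against 7: 0 / +6 / -9.
- 16 against 3: +9 / +17 / -14.
- 19 against 3 with patients differing in responsiveness (beta-binomial, mean 0.55, assumed intraclass correlation 0.3): 0.974 against 0.805, 0.569 against 0.559, 0.231 against 0.285, so +17 / +1 / -5.

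**Plain per-request rate.** Let a be the response to in-programme requests and c the response to shared PROMs, the same in both arms. For 19 against 3, intervention is (16a + 3c)/19 and control is c. The gap is (16/19)(a - c) = 0.842(a - c). It is zero if a = c, and about 8 points for each 10 points by which they differ.

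**Precision under the fix.**

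- Single-arm 95% half-width at 0.55 with 100 patients: 1.96 × √(0.55 × 0.45/100) = 0.098.
- Between arms, 100 per arm, two-sided 0.05, 80% power, pooled-variance normal formula: the detectable difference is 0.197, 0.182 or 0.134 at an assumed control completion of 0.40, 0.60 or 0.80.

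**The case against.** The best defence is that the shared set is what the authors mean. The Data Analysis paragraph puts response rates and PROM scores in one between-arm test. PROM scores can be compared between arms only before and after the programme, so response rates might be read under the same limit. What stands of this is that a shared set exists and the text is ambiguous. It does not settle the matter: nothing states the limit, and the Methods wording treats PGHD and check-ins as requests.

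It can also be said that this is a feasibility pilot. That tempers the severity, but the section specifies a randomised comparison with hypothesis tests, an alpha level and 80 to 90% power.

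The numerical objection is sound as far as it goes. The gaps depend on thresholds, response rates and a correlation that the plan does not give, and a plain per-request rate has no gap when response is equal across request types.

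A reader might infer three stronger things that the documents do not support:

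- That controls get no data requests, so no comparison is possible. They are asked for three PROMs and a weighing, before and after.
- That the comparison is biased in favour of the intervention. The sign changes with the definition and the response level.
- That the whole primary outcome fails. PAM-13 is collected before and after in both arms.

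**Conclusion.** The point holds as a gap in definition that should be fixed. Section 3.4.2 tests response rates between arms, describes the PGHD and monthly PROM requests for one arm only (and probably the check-ins, though their sentence names no arm), and does not confine the test to the requests both arms share.

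The textual finding needs no modelling. The counts of 22 against 6 and 19 against 3 rest on the two stated assumptions about check-ins and the last monthly PROMs. The illustrated gaps, +9, +10 or -16 points at a common response of 0.55, show what an open definition allows and are not a forecast. For scale, the planning proportions 0.55 and 0.40 are 15 points apart.

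**What to change.** Choose one of two repairs, of equal standing, before enrolment:

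1. Limit any between-arm response-rate test to requests made to both arms. One example is completion of all three post-intervention PROMs within a set window, with the per-patient definition fixed in advance and randomised patients lost to follow-up counted as non-responders.
2. Drop the between-arm response-rate test and use PAM-13, already collected before and after in both arms, as the between-arm engagement measure.

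In either case, report response to monthly PROMs, check-ins and PGHD requests for the intervention arm only, as a proportion with a 95% confidence interval. State which arm receives the check-ins and whether the last monthly PROMs serve as the post-intervention PROMs.

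The change is to wording in the methods, outcomes, analysis and power paragraphs, with no new data. It has three costs:

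- In-programme response becomes a single-arm estimate, good to about ±10 points with 100 intervention patients.
- Under the first repair, post-intervention PROM completion partly measures retention, since it is paired with a clinic weighing.
- The measure chosen needs its own power basis. For post-intervention PROM completion with 100 per arm and 80% power, the detectable difference is about 13 to 20 points as assumed control completion goes from 0.80 down to 0.40.

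### Patient engagement, the primary outcome, is tested through three measures at one alpha of 0.05, with no named primary measure or success rule

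*Combined protocol and SAP*

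**What the plan says.** All of this is in section 3.4.2 (Specific Aim 2) of the combined protocol and SAP.

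- **Outcomes and measures.** Patient engagement is the primary outcome. "This outcome will be measured by patient response rates to data requests; by the frequency of unprompted messages sent by patients to research personnel"; the sentence then adds PAM-13 performance as a third measure.
- **Data Analysis.** "Logistic regression or the Chi-square test of proportions will be used to test differences in response rates and PROM scores". The PAM-13 is one of the PROMs, so this covers two of the three measures. For the third, unprompted messages, the distribution is assessed first and the count is then "either analyzed using Poisson regression or dichotomized based on a clinically relevant cut-off". Neither a criterion for the switch nor a cut-off value is given.
- **Power.** The calculation concerns a "proportional difference of 20% (0.55 intervention; 0.40 control) in the primary outcome", with alpha 0.05, totals of 256 (90% power) and 192 (80% power), and 200 enrolled (100 per arm) regarded as adequate. Which of the three measures this proportion represents is not stated.
- **Methods, on who is asked for what.** "Intervention patients will be asked to track PGHD elements related to weight management through a mobile health app loaded on their phones", and "Intervention patients will also be asked to complete the three PROMs once each per month". By contrast, "Both intervention and control patients will be weighed on a clinic scale and asked to complete three PROMs pre- and post-intervention".

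The text available for review defines no composite of the three measures, no any-one or all-three rule, and no multiplicity adjustment.

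**The concern.** Engagement is a construct, not a variable. Three measures with three between-arm tests can support a claim about it in several ways, and the operating characteristics depend on which way is meant. If one significant result out of three is enough, the chance of a false positive exceeds the stated 5%. If all three are required, the stated power, which is for one comparison, does not apply. The two readings fail in opposite directions, and a reader of the plan cannot tell which was intended.

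The power paragraph does not settle the matter. It uses a proportion, which might suggest the response rate. But a dichotomised message count is also a proportion, and assigning logistic regression or chi-square to PROM scores implies that the PAM-13 may be dichotomised too. The response rate also needs definition before it can be compared, because most data requests go to the intervention arm only.

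At stake is the conclusion on the Aim 2 hypothesis that the intervention improves engagement.

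**Working it through.** **1. The plan's own figures.** Inputs from the Power paragraph: alpha 0.05 (sidedness not stated), equal arms, power 90% and 80%. The pooled two-proportion formula per arm, with p̄ the mean of the two rates, is

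n = [1.960 × √(2p̄(1−p̄)) + z(power) × √(p1(1−p1) + p2(1−p2))]² / (p1−p2)².

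- Printed rates 0.55 vs 0.40, two-sided: 231 and 173 per arm, total 462 and 346. These are not the stated 256 and 192.
- 0.55 vs 0.35 (a 20-point difference), two-sided, p̄ = 0.45: at 90%, (1.960 × 0.7036 + 1.2816 × 0.6892)² / 0.04 = 127.9, so 128 per arm and 256 in total. At 80%, (1.960 × 0.7036 + 0.8416 × 0.6892)² / 0.04 = 95.9, so 96 per arm and 192 in total. Both stated totals are reproduced.

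The mismatch between the printed rates and the totals is a separate issue. It matters here only because power must be quoted for a specific pair, so both are shown.

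Power for one measure at 100 per arm is Φ[(|p1−p2| × √100 − 1.960 × √(2p̄(1−p̄))) / √(p1(1−p1) + p2(1−p2))]:
- 0.55 vs 0.35: Φ[(2.000 − 1.379)/0.689] = Φ(0.901) = 82%.
- 0.55 vs 0.40: Φ[(1.500 − 1.384)/0.698] = Φ(0.166) = 57%.

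**2. Any-one rule.** For three independent tests the two-sided family-wise error is 1 − 0.95³ = 14.3%. In the direction of benefit it is 1 − 0.975³ = 7.3%, against 2.5% for one test. For correlated tests, one million draws from a trivariate normal with equal pairwise correlation were used (table below).

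**3. All-three rule.** Power comes from the same trivariate normal, each test centred to give the single-measure power above. This assumes equal effects on all three measures. With independence it is the cube: 0.816³ = 54% and 0.566³ = 18%.

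| Correlation | Any-one error, two-sided | All-three power, 0.55 vs 0.35 (single 82%) | All-three power, 0.55 vs 0.40 (single 57%) |
|---|---|---|---|
| 0 | 14.3% | 54% | 18% |
| 0.3 | 13.6% | 60% | 26% |
| 0.5 | 12.5% | 64% | 31% |
| 0.7 | 10.9% | 68% | 38% |
| 0.9 | 8.3% | 74% | 46% |

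False claims of benefit under the any-one rule are 7.3%, 6.8%, 6.2%, 5.4% and 4.1% down the same rows.

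Error under the all-three rule depends on which measures are truly unaffected. If none is affected it is far below 5% (2.2% at correlation 0.9). If two measures truly and strongly improve and the third does not, it approaches 5% at every correlation from 0 to 0.9. The bound is therefore 5%.

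**4. Message counts.** The documents give no mean or dispersion, so these figures rest on assumptions: negative binomial counts, 100 per arm, no true difference, mean 2, variance/mean 1.5, 2, 3 and 5. Plain Poisson kept despite overdispersion has error of 11%, 17%, 26% and 38%. But a pooled dispersion check flags 98-100% of such data sets, and moving to a fixed cut-off of at least one message then gives 5.0-5.4%. Poisson with robust variance gives 5.1-5.7% at mean 2, but 6.2% and 7.3% at mean 0.5 with variance/mean 3 and 5.

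**The case against.** The strongest reply is that this is a pilot meant to show feasibility, so several indicators of one construct may be reported side by side without a confirmatory rule. Nowhere does the plan say that success on one measure would be declared a success for engagement. That stands in part: it limits how serious the gap is. It does not close it, because the plan also states a directional hypothesis, an alpha, two power levels and an enrolment at which it regards itself as adequately powered.

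Three stronger readings are tempting and are not supported:

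- A reader might infer that the trial has a 14.3% chance of falsely claiming benefit. That figure counts significant results in either direction, assumes independence, and applies only under an any-one rule. The benefit-direction figure is 7.3% at most.
- A reader might infer that the all-three rule pushes error well below 5% in general. The low values hold only when no measure is affected.
- A reader might infer that the message-count analysis is invalid, or that a cut-off would be picked after seeing results by arm. The plan assesses the distribution before choosing a method, which is a safeguard, and a cut-off fixed in advance keeps error near 5%. Nothing in the text plans an outcome-driven choice, and describing the cut-off as clinically relevant points to a clinical basis. What remains is that the cut-off and the switching criterion are not stated.

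**Conclusion.** The point holds. The plan attaches one alpha and one power figure to an outcome with three separately tested measures, and does not say which measure, or what combination, decides. Under an any-one rule two-sided error is 14.3% to 8.3% across correlations 0 to 0.9. Under an all-three rule error is controlled, but power at 100 per arm drops from 82% to about 54-74% for the pair that reproduces the stated totals, and from 57% to about 18-46% for the printed pair.

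These sizes rest on equal pairwise correlation, normal approximations and, for power, equal effects; the documents give no correlation between the measures. The feasibility setting makes this something that should be corrected rather than a fatal flaw. The count model is a minor supporting point, and its error rates are illustrations only.

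**What to change.** Before arm-level data are seen, name the one engagement measure that carries the two-sided 0.05 test. Define it as a patient-level proportion that matches the power statement and rests on data requested of both arms. Report the other two as supportive, with 95% confidence intervals. The definition depends on the choice:

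- **Response rate:** restrict it to requests made of both arms. Those expressly common to both are the pre- and post-intervention PROMs and the weighing.
- **PAM-13:** state the threshold that a logistic or chi-square analysis needs.
- **Unprompted messages:** state the cut-off that turns the count into a proportion.

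The cost is that two measures lose primary status and a binary endpoint must be fixed in advance. A response rate valid in both arms is close to a retention measure. No extra patients are needed for multiplicity.

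Alternatively, apply Holm across the three and restate the power. At 100 per arm the first step (0.05/3 = 0.0167) gives a per-measure floor of 68% for 0.55 vs 0.35, or 39% for 0.55 vs 0.40. With three equally effective measures at correlation 0 to 0.5, the later steps raise this to about 76-77% or 46%, against 82% or 57% for one named measure.

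Minor: if message counts are modelled and prove overdispersed, use negative binomial or robust-variance Poisson regression instead of plain Poisson. Or keep the dichotomised analysis, with its cut-off and switching criterion fixed in advance. This is a wording change. Intervals widen relative to plain Poisson by √(variance/mean) − 1, for example √2 − 1 = 41% at a ratio of 2, which is the width that the data warrant.

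### Baseline adjustment hangs on a p<0.05 balance test, so a PROM's own baseline score is left out in about 95% of trials, at a cost in power

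*Combined protocol and SAP*

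**What the plan says.** All the relevant text is in section 3.4.2 of the combined protocol and SAP.

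- **Adjustment rule (Data Analysis):** if differences at p<0.05 "are found between the groups for demographic or baseline measures, these will be controlled for in subsequent analyses". No covariate is named for any PROM model.
- **Test for PROMs (Data Analysis):** "Logistic regression or the Chi-square test of proportions will be used to test differences in response rates and PROM scores" between the arms. No baseline term is mentioned, and a Chi-square test cannot hold one.
- **Data available (Methods):** "Both intervention and control patients will be weighed on a clinic scale and asked to complete three PROMs pre- and post-intervention". The three are PAM-13, HRQOL-4 and the Healthy Days Symptoms Module.
- **Role of the PROMs (Outcomes and measures):** PAM-13 is one of three measures of patient engagement, the primary outcome, and is described only as performance. For the others, "Secondary outcomes include weight loss and performance on the HRQOL-4 and Healthy Days Symptoms PROMs pre- and post-intervention".
- **Size (Power):** the plan aims for 300 patients but accepts 200, at 100 per arm, as adequate.

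**The concern.** In a randomised trial, baseline differences between arms arise by chance. A test at the 5% level therefore picks out any one baseline measure in about 5% of trials, whether or not that measure predicts the outcome. Precision, however, comes from adjusting for variables that predict the outcome, and a PROM's own baseline score will usually be one of the strongest candidates. The rule thus selects on the wrong property.

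What is at stake is power for the PAM-13, HRQOL-4 and Symptoms Module comparisons. Validity is not at stake: the rule does not push the false-positive rate above its nominal level to any material extent. Response rates and unprompted messages have no pre-intervention value, and weight is already analysed as change, so these outcomes are little affected.

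There is a second, smaller consequence. If logistic regression is used, a chance baseline p-value decides whether an unadjusted or an adjusted odds ratio is reported, and these are different quantities.

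**Working it through.** **Inputs from the documents.** Trigger p<0.05; 100 per arm (the enrolment floor); alpha 0.05, taken as two-sided; and the effect used for the sample size, "to detect a proportional difference of 20% (0.55 intervention; 0.40 control) in the primary outcome".

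**Inputs assumed.** The pre-post correlation r is not in the documents, so 0.3, 0.5 and 0.7 are shown. No PROM cut-off or PROM effect is given either, so the sample-size rates are borrowed for the PROMs. Follow-up is taken as complete.

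**1. The plan's own figures.** Per arm, n = [1.96·√(2p̄(1−p̄)) + z_power·√(p₁(1−p₁)+p₂(1−p₂))]² / (p₁−p₂)².

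- 0.55 vs 0.40 gives totals of 346 (80% power) and 462 (90%), not the stated 192 and 256.
- 0.55 vs 0.35 gives exactly 192 and 256.

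The printed rates and the stated 20% difference disagree. That is a separate matter, so both readings are carried forward.

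**2. How often the rule acts.** In 20,000 simulated trials per cell, a t-test on the baseline score gave p<0.05 in 4.7% to 5.2% of trials. The 5% is per measure: with several measures tested, the chance that at least one triggers is higher, but that does not bring in the others.

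**3. Power with the stated tests.** The latent post score is r × baseline + √(1−r²) × noise + effect, cut to give the control rate. The rule means an unadjusted test unless the baseline t-test gives p<0.05, and then a baseline-adjusted test. The comparator is logistic regression that always holds the baseline score.

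| Rates | r | Rule | Always adjusted | Gain (points) |
|---|---|---|---|---|
| 0.55 vs 0.40 | 0.3 | 58.3% | 58.8% | 0.5 |
| | 0.5 | 59.0% | 63.8% | 4.8 |
| | 0.7 | 59.7% | 73.2% | 13.5 |
| 0.55 vs 0.35 | 0.3 | 82.9% | 83.5% | 0.6 |
| | 0.5 | 82.6% | 87.3% | 4.7 |
| | 0.7 | 84.0% | 93.4% | 9.4 |

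A repeat with 6,000 trials per cell at 0.55 vs 0.40 gave 59.6/59.5/60.6% under the rule and 59.6/64.3/73.8% always adjusted.

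**4. Precision.** At 0.55 vs 0.40, the SD of the risk difference is 0.0699/0.0682/0.0664 under the rule and 0.0684/0.0640/0.0574 for a standardised risk difference from the adjusted model. The ratios are 1.02, 1.07 and 1.16. Both estimators average 0.150. Odds ratios cannot be compared in this way: the mean log odds ratio is 0.61 unadjusted but 0.65/0.74/0.92 adjusted.

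**5. If scores are analysed as continuous.** The effect is probit(0.55) − probit(0.40) = 0.38 SD, or probit(0.55) − probit(0.35) = 0.51 SD. ANCOVA reduces the residual variance to 1 − r², that is 0.91/0.75/0.51.

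- 0.38 SD: rule 76/77/78%, ANCOVA 79/87/96%.
- 0.51 SD: rule 95/96/96%, ANCOVA 96/99/99.9%.
- Change scores at 0.38 SD, with variance factor 2(1 − r): 62/76/93%.

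**6. False positives under the rule.** For a dichotomised score 5.5/4.8/4.7% (plain Chi-square in the same runs 5.6/5.4/5.6%); for a continuous score 4.7/4.2/3.5%. The rule is not inflationary, and it becomes conservative as r rises.

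**The case against.** The strongest reply is that silence is not exclusion. The plan does not list the terms of its logistic model. It collects PROMs before and after, it attaches pre and post to two of them, and its Aim 2 hypothesis speaks of improvement. If change scores are intended, baseline already enters by subtraction. It is true that the documents leave this open. But no change model is stated for any PROM, and the only adjustment rule that is stated is the p<0.05 trigger. On the change-score reading ANCOVA still has more power, by about 18, 11 and 3 points at r = 0.3, 0.5 and 0.7 (0.795−0.616, 0.869−0.759, 0.961−0.930). That loss would come from the choice of change scores, not from the trigger.

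The size can also be challenged, and here part of the objection stands:

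- If the baseline score is dichotomised like the outcome, the gains at 0.55 vs 0.40 fall to about 0/3/9 points.
- If the target of 300 is reached (150 per arm), the gains at 0.55 vs 0.35 are only about 0/2/4 points; at 0.55 vs 0.40 they remain about 0.5/4.5/12.
- The PROM effect and r are both assumptions.

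Finally, this is a feasibility study, and the issue is efficiency. That limits the severity. But the plan does specify between-arm tests and a threshold for adequate power, so using data already in hand is worthwhile.

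**Conclusion.** The concern holds. The stated rule brings a PROM's own baseline score into its comparison in only about 5% of trials, and it recovers almost none of the available precision. At 100 per arm with the stated tests, always adjusting adds about 0.5 points of power at r = 0.3, 5 points at r = 0.5, and 9 to 13.5 points at r = 0.7. With continuous scores and a 0.38 SD effect, the gains are about 3, 10 and 18 points. These sizes rest on the assumed r, on sample-size rates borrowed for the PROMs, on complete follow-up, and on a baseline score kept continuous. They are smaller with a dichotomised baseline score, or at full recruitment under the 0.55 vs 0.35 reading. No conclusion of the trial is invalidated. This is an avoidable loss on one measure of the primary outcome and on two secondary outcomes, and it should be corrected.

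**What to change.** 1. Delete the p<0.05 trigger and report baseline balance descriptively.
2. State in advance that each model for PAM-13, HRQOL-4 and the Symptoms Module contains arm and the baseline value of the same measure, whatever the observed balance.
3. Where a PROM is dichotomised, use baseline-adjusted logistic regression in place of Chi-square, and report a standardised risk difference so that the reported quantity is clear.

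As a separate choice, a linear model (ANCOVA) on the continuous score is preferable where the score allows it. Baseline weight or BMI in the weight model is optional, with small gain.

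The cost is a change of analysis wording. No new data are needed, because the baseline PROMs are already planned in both arms. If r turns out to be low, almost nothing is lost by adjusting.
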